Master Thesis Proposal

Protocol Title: Comparison of the effectiveness of positioning device cotton roll-coated viscoelastic polymer pads versus viscoelastic polymer pads for preventing pressure injuries in patients undergoing lumbar spine surgery

Applicant Organization: Central Taiwan University of Science and Technology

Department of Nursing

Principal Investigator(s): _____ sign:

Co-Investigator(s): _____ sign:

Fill out date:

head record

page number

I.	Summary	
II.	Contents of the proposal	
1.	Test background.....	02
2.	Subject of the experiment.....	03
3.	Purpose of the test.....	03
4.	Research object.....	05
	(1) Inclusion and exclusion conditions	
	(2) Number of subjects	
	(3) Recruitment sources and methods	
	(4) Protection of the rights and interests of research subjects and methods of informed consent	
5.	Test method.....	06
	(1) Criteria and number of test subjects	
	(2) Test design and method	
	(3) Test period and progress	
	(4) Tracking or rehabilitation plan	
	(5) Evaluation and statistical methods	
	(6) Subject tracking and necessary care plan	
6.	Anticipated test results.....	11
7.	possible harm andplaceReasoning.....	12
8.	Scheduled progress.....	14

(Please summarize the purpose, implementation method, expected research results and key words of this project)

Research Background: Pressure injury (pressure injuries, PI) is one of the common complications in surgery, which means PI that occurs immediately after surgery or within hours to 3 days after surgery. The incidence of PI in spinal surgery is about 5%~66%.

Purpose: This study compares the differences in PI in patients undergoing lumbar spine surgery when the positioning device uses cotton roll-coated viscoelastic polymer pads and viscoelastic polymer pads.

Research methods: In this study, the split-body design was adopted as an experimental study of random assignment, and the four parts of the patient's body that were in contact with the positioning device (left chest, left iliac crest and right chest, right iliac crest) were randomly assigned to In the experimental group or the control group, compare the decompression effect of different materials on the positioning device on the patient; the experimental group uses the positioning device ReltonHall prone frame 3 cm cotton roll-coated viscoelastic polymer pads, and the control group uses the positioning device ReltonHall prone frame viscoelastic polymer pads. The research object is lumbar surgery patients in the operating room of a hospital in the north. It is expected to enroll 50 people. The experimental group or the control group will be assigned by random number table. the measurement time is before operation, immediately after operation, 30 minutes after operation, 24 hours after operation, and 48 hours after operation. This study uses SPSS 25.0 Chinese version package software for data analysis, descriptive statistics use frequency, percentage, average value, standard deviation, etc., and inferential statistics use independent sample t test, chi-square test, generalized estimating equation, etc. to analyze data.

Keywords: lumbar spine surgery, pressure injury, positioning device, preventive, split design

II. the content of the plan

1. Research background:Please describe the background and importance of this plan. The content can be written with reference to the following points: (1) Policy or Legislative basis (2) Problem situation or development requirements (3) Literature research on related research at home and abroad or this plan (4)Relevance of health care. (page limit 5 pages)

Research background and motivation

Pressure injuries (pressure injuries, PI for short) are one of the common complications in surgery, which means pressure injuries that occur immediately after surgery or within a few hours to 3 days after surgery. Most of the pressure injuries occur In grades 1 to 2 (Tang et al., 2021); while the incidence of pressure injuries in spinal surgery is between 5% and 66% (Kwee et al., 2015), reports in the United States show that each The average cost of treatment for patients with pressure injuries is US\$10,708, with a total annual cost of more than US\$26.8 billion (Padula & Delarmente, 2019); it is pointed out in Chinese literature that the cost of treating a patient with pressure injury is about NT\$7,000-80,000 Yuan (Chen, 1998); Intraoperative pressure injuries will increase patients' complications, hospitalization time and medical expenses, thus negatively affecting the postoperative recovery care of patients and their families. The operating room is an important place to prevent intraoperative pressure injury, so it is important for the nurses in the operating room to provide effective nursing measures to prevent pressure injury, which can reduce the risk of pressure injury and the cost of nursing; for the hospital, the operation process can reduce The incidence of pressure injuries of patients can reduce medical resources and labor costs, and provide patients with a safe medical environment and good medical quality.

Regarding the prevention of the incidence of pressure injuries in patients undergoing spinal surgery, in the study of Wu et al. (2011), the decompression materials on the positioning devices (Positioning Devices) of patients undergoing spinal posterior surgery were compared using The effect of high-density foam pad (High-Density Foam Pad, HDFP) viscoelastic polymer pads (Viscoelastic Polymer Pads, VPP) on preventing the incidence of pressure injury. The research results show that although the pressure of skin contact with VPP is significantly lower than that of contact with HDFP, the The effect of preventing the incidence of pressure injury is not significant. The research suggests that when the risk of pressure injury is high in patients undergoing spinal surgery, the fat pad should be considered for the prevention of pressure injury; Zhang et al. In the improvement plan for the incidence of pressure injury in surgical patients, it is suggested that the cotton roll-coated with the viscoelastic polymer pads material can prevent the incidence of pressure

injury, but it does not describe how many layers of the cotton roll need to be coated for the best effect, and its effect has not been verified; In addition, Dai et al. (2022) mentioned in the combined care plan for the prevention of intraoperative pressure injury in surgical patients that the posture of prone surgery can be used to cover the viscoelastic polymer pads with cotton rolls to protect the skin. The article does not detail how many layers of cotton are covered The effect of viscoelastic polymer pads on preventing pressure injuries is the best, and it has not been explained how its single effect is? According to the author's clinical experience, although the intraoperative positioning device (Relton-Hall prone frame) for spinal patients undergoing surgery in the prone position uses viscoelastic polymer pads to prevent pressure injuries , but patients still often suffer from pressure injuries. Therefore, the author explores whether wrapping the fat pad of the positioning device with cotton rolls can reduce the incidence of pressure injuries; The effect of covering fat pad and fat pad material in preventing pressure injury in lumbar spine surgery.

2. Purpose of the test:Please list in detail the goals to be achieved in this plan and the work items to be completed. Avoid empty space.
lack of narrative. For a plan with a period of more than one year, the overall goal of the whole plan and the plans for each year should be listed
purpose. (page limit 2 pages)

Research purposes

For patients undergoing spinal posterior surgery (spinal posterior surgery), the decompression material of the intraoperative positioning device (Relton-Hall prone frame) is used to wrap the fat pad and fat pad material with cotton rolls. Is there a difference in the rate.

3. Test object: The content includes the following points for writing: (1) Inclusion and exclusion conditions (2) Number of subjects (3) Recruitment sources and methods (4) Protection of research subjects' rights and methods of informed consent. (page limit 5 pages)

research object

Patients with lumbar spine surgery in the operating room of a hospital in the north are eligible for inclusion as follows:

1. Patients who underwent lumbar nerve decompression combined with internal fixation and bone fusion.
2. Take the prone position using the ReltonHall rack.
3. The operation time is greater than 2.5 hours.
4. The surgical anesthesia is general anesthesia.
5. Routine surgery registered in the surgery schedule.
6. Before the operation, the skin was intact and there was no pressure injury.

Exclusion criteria as follows:

1. Patients undergoing emergency lumbar surgery.
2. Are younger than 18 years old.
3. The operation time is less than 2.5 hours.
4. Preoperative skin incompleteness (obvious chest and iliac crest pressure phenomenon).
5. Percutaneous minimally invasive disc herniation decompression (percutaneous endoscopic lumbar disc, PELD).

Sample Size Estimation

The author refers to the research results of Yang et al. (2020) to estimate the sample size, estimates with G-power 3.1 software, sets the significance level of α value to 0.05, and the test power is 0.80, using the ratio of two groups (chi-square test) To test the sample size, the minimum sample size for this study was determined to be 93 people. According to the estimated number of samples and pre-test results in the above literature, it is planned to collect 93 people. After correcting the sample loss rate, 100 people will be recruited. Since this study adopts a split test (self-experimental group and control group), it is estimated that Enroll 50 people.

research ethics

To follow the principles of patient autonomy, non-injury and confidentiality, before the research is conducted, the purpose and process of the research must be explained to the research subjects or their families, and the patients can request to stop at any time during the research process without affecting the future medical rights and safety. Before the implementation of this study, it is expected to be submitted to the Human Research Ethics Committee of a medical center in central China for review; the data of the research subjects will only be used for academic research to protect the privacy of the research subjects.

4. Research method:The content includes the following points for writing: (1) The standard and number of subjects to be tested (2) The design and method of the test (3) The duration and progress of the test (4) Tracking or rehabilitation plan (5) Evaluation and statistical methods (6)) Tracking of subjects and necessary care plans.

Research design

This study adopts the split-body design (left chest, left iliac crest and right chest, right iliac crest) as an experimental study, comparing two kinds of decompression materials (positioning device ReltonHall prone frame The effect of wrapping the fat pad with a cotton roll on one side and the fat pad on the other side) in reducing pressure injuries. The split design is that each patient is an experimental group and also a control group to remove biological variability, such as demographic characteristics: potential factors such as gender, age, disease history, nutritional status, and overall health status. It is expected to understand the effect of the ReltonHall cotton roll-coated fat pad and the fat pad on the incidence of postoperative pressure injury and the decompression effect of patients undergoing lumbar spine surgery.

Research Design Patterns

group	Pretest	intervention	Posttest I immediately	Posttest II 30 minutes	Posttest III 24 hours	Posttest IV 48 hours
Experimental side	O1	X1	O2	O3	O4	O5
control side	O1	x	O2	O3	O4	O5

Note:

O1: After general anesthesia, the subject was placed supine to measure the integrity of the skin.

X1: Refers to the experimental side chest and iliac crest positioning device ReltonHall fat pad wrapped cotton roll 3 cm.

X: Refers to the ReltonHall, the positioning device of the chest and iliac crest of the control group, which is the fat pad routine.

O2: Immediately after the operation, I was measured after the pressure injury was graded on the experimental side and the control side.

O3: 30 minutes after the operation, the experimental side and the control side were tested for pressure injury grade II.

[figure not shown]
O4: 24 hours after the operation, the experimental side and the control side were tested for pressure injury grade III.

O5: 48 hours after the operation, test the IV after the pressure injury grade was carried out on the experimental side and the control side.

Positioning and intervention methods

The patient enters the operating room, and the four support cushions on the frame have been disposed in advance according to the experimental side and the control side. After general

anesthesia, the surgical team uses standard positioning steps to measure the body length: from the 2 cm mark point of the armpit to the iliac side. between the bony crests; and body width: between the two iliac crests, then adjust the patient's posture and the contact surface of the prone frame according to the markings on the ReltonHall prone frame support pads to ensure that the pressure points on the patient's body are consistent with the marked points; place the patient Lie prone on the ReltonHall prone frame. After the patient is in the prone position, the horizontal line between the scapula and the posterior iliac crest must be parallel to the ground.

1. Experimental side intervention method

Viscoelastic polymer pads (Viscoelastic Polymer Pads) (model 40700; Action, Hagerstown, MD) were used on the 4 support columns of the Relton-Hall prone frame of the positioning device. The dimensions were: 18 cm long, 15 cm wide, and 2 cm thick. The fat pad accessories are designed to cover the four support columns of the Relton-Hall prone frame. The fat pad of the chest and iliac crest on the same side on the Relton-Hall prone frame is covered with a cotton roll for 3 cm. The skin is the experimental side.

2. Control Side Intervention Method

In addition to the experimental side, the fat pad of the chest and iliac crest on the other side of the Relton-Hall prone frame, and the patient's skin contact position is the control side.

Pressure injury record form, this record form is based on the wound evaluation indicators jointly developed by the National Pressure Ulcer Advisory Committee (NPIAP, 2016) and the European Pressure Ulcer Advisory Panel (EPUAP), according to the established Designed according to pressure injury grading standards.

According to this record sheet, the recorded pressureing conditions are divided into "pre-operative assessment", "immediately post-operative assessment", "30-minute post-operative assessment", "24-hour post-operative assessment", and "48-hour post-operative assessment". Nursing staff in the ward and wards should evaluate and record the pressure points that may cause pressure injuries. Including the site of occurrence and the grade of pressure injury. In order to increase the accuracy of the evaluation, the classification and description of the pressure injury are provided at the bottom of each record sheet for reference.

Statistical analysis methods for various data

data item	Statistical analysis method
1. Basic information of subjects: 1. Gender, age, suffering from chronic diseases, BMI, operation time, albumin, intraoperative body temperature, and intraoperative blood pressure.	1. Described in terms of times, percentages, etc. 2. Chi-square was used to test whether there was a significant difference between the experimental group and the control group.
2. Age, days of pressureing.	1. Described by means, standard deviations, etc. 2. Independent sample t test was used to test whether there was a significant difference between the experimental group and the control group.
2. The pressured parts of the two groups of subjects (one-sided chest, iliac crest), whether there is PI in the compressed parts of the two groups, the contact point of one-sided chest and iliac crest (experimental group), the other side of the chest, The contact point of the iliac crest is (control group)	Independent sample t was used to test whether there were significant differences between the experimental group and the control group immediately after operation, 30min, 24hr, and 48hr.

3. To test whether there are significant differences due to time factors between the two groups of subjects under the decompression material immediately after the operation, 30min, 24hr, and 48hr.

Test the experimental group and the control group by the generalized estimating equation

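### Left/right side is neither balanced in the stated allocation nor included in the planned model; doing both is a cheap gain in precision, not the cure for a bias

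*Protocol*

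**What the plan says.** **Allocation.** The Summary (Research methods) states that "The experimental group or the control group will be assigned by random number table". No left/right ratio, blocking or balancing is given. "It is expected to enroll 50 people", so there are 50 pairs of sides.

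**Unit allocated.** The Summary lists the contact areas as "left chest, left iliac crest and right chest, right iliac crest) were randomly assigned to" one group or the other, which can be read as four separate draws per patient. Section 4 describes a whole-side allocation instead. Under Positioning and intervention methods, "The fat pad of the chest and iliac crest on the same side" receives the cotton, and the opposite side is the control.

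**Reason for pairing.** Research design says: "The split design is that each patient is an experimental group and also a control group to remove biological variability". The examples that follow are all patient-level: sex, age, disease history, nutrition and general health.

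**Analysis.** The table of statistical methods compares pressure injury between the sides by an independent-sample t test at each time. It uses a GEE for group, time and their interaction. Left/right appears in none of its items.

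**Positioning.** The same section has the pads adjusted to marked points and the trunk levelled on the frame.

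**The concern.** In a split-body trial, left/right plays the part that period plays in a crossover. It varies within the patient, so using each patient as their own control does not cancel it. If one side of the frame carries more risk across patients, two things follow:

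- Unless the allocation happens to be 25:25, part of that risk difference enters the unadjusted cotton estimate in the one allocation actually drawn.
- Even at 25:25, the side difference stays in the residual variation of an analysis without a side term, so the standard error is larger than it need be.

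The stake is precision in a study of only 50 patients.

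**Working it through.** **The plan's own figure.** The protocol "sets the significance level of α value to 0.05, and the test power is 0.80", and "the minimum sample size for this study was determined to be 93 people". No effect size or event rates are given, so the 93 cannot be confirmed or refuted. Working backwards, it corresponds to w = (1.960 + 0.842)/√93 = 0.2905 for a 1-df chi-square. The step to 100 implies about 7% loss (93/0.93 = 100), and halving gives 50 patients. Only the 50 is used below.

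**Inputs from the protocol.** 50 patients, whole-side allocation, random number table, no side term.

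**Assumed inputs.** An unrestricted 1:1 draw; left-right risk difference d of 5, 10 or 20 points; injury risk p of 20-30%; between-side correlation ρ of 0.3-0.5. The power figures use 35% control risk, latent correlation 0.5 and a 20-point cotton effect.

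**Step 1: chance imbalance.** Let L be the number of patients with cotton on the left, L ~ Binomial(50, 0.5).
- P(exactly 25:25) = 11.2%
- P(30:20 or worse) = 2·P(L ≥ 30) = 20.3%
- P(32:18 or worse) = 2·P(L ≥ 32) = 6.5%

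**Step 2: shift in an unadjusted estimate.** Shift = d × (2L/50 − 1).
- At 30:20 the factor is 60/50 − 1 = 0.20, so d = 5, 10, 20 gives 1, 2, 4 points.
- At 32:18 the factor is 64/50 − 1 = 0.28, giving 1.4, 2.8, 5.6 points.
- Over all draws the mean shift is 0 and its SD is d/√50 = 0.141d: 0.7, 1.4, 2.8 points. The sampling SD of the cotton effect itself is about 7 to 8 points.

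**Step 3: added variance.** Ratio = (d²/50) / (2p(1−p)(1−ρ)/50) = d² / [2p(1−p)(1−ρ)]. Over the assumed grid the denominator runs from 2(0.2)(0.8)(0.5) = 0.16 to 2(0.3)(0.7)(0.7) = 0.294.
- d = 5: 0.0025/0.294 = 0.9% to 0.0025/0.16 = 1.6%
- d = 10: 0.01/0.294 = 3.4% to 0.01/0.16 = 6.3%
- d = 20: 0.04/0.294 = 13.6% to 0.04/0.16 = 25%

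**Step 4: power.** Simulation of 50 pairs, paired t test on the side differences, 60,000 runs per setting.

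| Side difference | Simple draw, no term | 25:25, no term | 25:25 with side term | Gain, first to last |
|---|---|---|---|---|
| 5 points | 77.1% | 77.5% | 78.2% | 1.1 |
| 10 points | 76.3% | 76.4% | 78.6% | 2.3 |
| 20 points | 71.9% | 73.4% | 78.9% | 7.0 |

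With no side difference, the full remedy costs nothing (77.8% against 78.2%).

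**Step 5: error rate.** In a paired (McNemar) analysis, the simple draw gives a type I error of 4.6% to 5.2% for side differences of 0 to 20 points. Balancing without the term makes the paired test conservative at a 20-point difference (3.7%), because the variance estimate still contains the side variation that balance has removed from the estimate.

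**The case against.** The case against is substantial, and much of it stands.

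- **No left-right risk difference is documented.** Every size of d above is an assumption, and the levelling and marked contact points are meant to keep any such difference small.
- **The lack of balance is inferred from silence.** A random number table can also be used to draw permuted blocks. An allocation procedure or analysis plan that is not shown could supply both the blocks and the side term.
- **The gain from balance alone is trivial.** Without the side term it is 0.1 to 1.5 points of power in the table above.

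Four stronger readings are tempting, and the protocol does not support them:

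1. *Bias or a false-positive risk.* Random choice of side makes the estimate unbiased over allocations, and a paired test stays near 5%.
2. *A shift that cannot be separated from the pad effect.* At 30:20 or 32:18, side and pad are only weakly associated, so a model with both terms separates them. The record form also captures the site of injury.
3. *Individual curvature as an example.* Its direction differs between patients, so neither a 25:25 list nor a left/right main effect removes it.
4. *Laterality as the only factor that pairing leaves.* That holds only under whole-side allocation. If the four areas were drawn separately, as the Summary can be read, chest against iliac crest would not be balanced within the patient either.

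What survives is narrower. The protocol sets out its analysis item by item and already commits to a GEE, so adding side is a concrete improvement on what it states.

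**Conclusion.** This is an optional, low-cost improvement in precision. The stated method is valid on this point if the sides are analysed as pairs. Its price is about 1, 2 or 7 points of power if left and right differ in risk by 5, 10 or 20 points, and nothing if they do not. The 20-point case is an extreme assumption; 5 to 10 points gives the more modest 1 to 2 points of power. These figures rest on an unrestricted draw, whole-side allocation, 35% control risk, latent correlation 0.5, a 20-point cotton effect and a paired analysis. The independent-sample tests that the table applies to paired sides are a weightier matter than this one.

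**What to change.** Before the first patient:

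1. Prepare an allocation list with 25 cotton-left and 25 cotton-right patients in random order, using permuted blocks of varying size.
2. Add left/right as a term in the GEE, with the patient as the cluster. Make both changes together: most of the gain comes from the term, and balance without it leaves the test slightly conservative. The term also covers any imbalance that arises through losses.
3. Reconcile the Summary's wording on four assigned areas with the whole-side allocation in section 4. The list above presumes the latter.

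The cost is one new list, one model degree of freedom and a slightly more predictable allocation, which varying the block sizes limits.

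### The pads are set up by side before the patient enters, but the only timed pre-operative skin check comes later, so the side can be known when a one-sided mark is judged

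*Protocol*

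**What the plan says.** - **Allocation.** Protocol, Summary, Research methods: "The experimental group or the control group will be assigned by random number table". No time of draw, holder of the list or concealment is given.
- **Set-up.** Protocol section 4, Positioning and intervention methods: on the patient's arrival in the operating room, "the four support cushions on the frame have been disposed in advance according to the experimental side and the control side". Anaesthesia and positioning follow.
- **Baseline skin check.** Protocol section 4, note to Research Design Patterns: "O1: After general anesthesia, the subject was placed supine to measure the integrity of the skin".
- **Skin eligibility.** Protocol section 3, inclusion item 6: "Before the operation, the skin was intact and there was no pressure injury". Exclusion item 4: "Preoperative skin incompleteness (obvious chest and iliac crest pressure phenomenon".
- **Record form.** Protocol section 4, description of the pressure injury record form: it lists a pre-operative assessment, without a time, ahead of the four post-operative ones. Nursing staff record site and grade. No masking is mentioned.
- **Unit of comparison.** Protocol section 4, Research design: "The split design is that each patient is an experimental group and also a control group".
- **A later criterion.** Protocol section 3, exclusion item 3: "The operation time is less than 2.5 hours". This can be settled only once the allocated pads are in use.

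**The concern.** Randomising the side protects the comparison only if eligibility and baseline skin state are settled without knowledge of the side. Here the side is physically set up before the one skin check that has a stated time. That check covers the same chest and iliac sites that are graded afterwards, and the protocol's background says most injuries are grades 1 to 2, so a faint baseline mark lies close to the outcome.

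Suppose a mark on the future cotton side leads to exclusion more readily than the same mark on the future control side. The retained control sides then carry more pre-existing redness, and cotton looks better with no true effect. Knowing the side can also colour the baseline record of patients who are kept. With 50 patients planned, a few discordant pairs can decide the result, and selective exclusions cannot be recovered from the data afterwards.

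**Working it through.** **Order of events.** Three facts follow directly from the text: the pads are arranged by side before arrival; O1 comes after induction; the skin criteria refer to the pre-operative state. Two links are not written: that O1 is where the skin criteria are decided, and that the person doing O1 can see the frame. The order permits side-aware judgement but does not establish it.

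**Why pairing does not settle it.** Excluding a patient removes both sides, so age, nutrition and other patient-level factors stay balanced. The decision to exclude may still depend on which side carries the mark, and pairing does not balance that.

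**Size under assumed rates.** The protocol gives no figure to reproduce here and no rate of baseline marks. All inputs below are assumptions, except the number of pairs, which comes from the stated minimum of 93 (93/2 = 46.5, rounded up to 47).

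- q: share of candidates with a one-sided mark, half on each side: 5%, 10%, 20%
- e_C, e_K: probability of exclusion when the mark is on the cotton or control side
- m: probability that a retained mark is later scored as an injury
- p: injury risk per side otherwise, 20% (10% on both sides) or 10% (5% on both sides), with no true effect

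Retained share of candidates: T = 1 − q + (q/2)(1 − e_C) + (q/2)(1 − e_K).
Marked sides among retained patients: k_C = (q/2)(1 − e_C)/T and k_K = (q/2)(1 − e_K)/T.
Spurious control-minus-cotton difference = m(1 − p)(k_K − k_C).

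Example with q = 10% and p = 20%; T = 0.95 in both scenarios:
- All-or-none (e_C = 1, e_K = 0, m = 1): k_C = 0, k_K = 0.05/0.95 = 5.26%; difference = 0.80 × 5.26 = 4.2 points.
- Partial (e_C = 0.75, e_K = 0.25, m = 0.5): k_C = 0.0125/0.95 = 1.32%, k_K = 0.0375/0.95 = 3.95%; difference = 0.5 × 0.80 × 2.63 = 1.1 points.

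Rejection is the two-sided mid-p McNemar test at 0.05 with 47 pairs, summed exactly over the possible discordant counts. With P11 the both-sides risk, the discordant probabilities are (1 − m·k_C − m·k_K)(p − P11) + m·k(1 − p), taking k = k_C for cotton-only and k = k_K for control-only injuries. The McNemar test is my choice for paired data, not the protocol's.

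| Injury per side | q | Partial: difference (points) | Partial: rejection | All-or-none: difference (points) | All-or-none: rejection |
|---|---|---|---|---|---|
| 20% | 0 | 0 | 4.1% | 0 | 4.1% |
| 20% | 5% | 0.5 | 4.2% | 2.1 | 5.0% |
| 20% | 10% | 1.1 | 4.4% | 4.2 | 7.9% |
| 20% | 20% | 2.2 | 5.2% | 8.9 | 20.0% |
| 10% | 0 | 0 | 2.3% | 0 | 2.3% |
| 10% | 5% | 0.6 | 2.7% | 2.3 | 4.5% |
| 10% | 10% | 1.2 | 3.3% | 4.7 | 10.3% |
| 10% | 20% | 2.5 | 5.2% | 10.0 | 32.3% |

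Simulation of 20,000 null trials agrees to within about half a percentage point (32.6% for the last cell).

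**A second model.** Keep all-or-none exclusion, but give a marked side a 60% injury risk and an unmarked side 20%, with 50 patients and the exact McNemar test. Expected rates are 20.0% (cotton) against 22.1% (control) at q = 10%, and 20.0% against 24.4% at q = 20%. Rejection is 3.4% and 5.2%, against about 3% with even-handed exclusion.

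**The case against.** A reader might infer that the protocol makes O1 the eligibility decision and so breaks allocation concealment outright. The text does not support that. O1 is defined as the pretest measurement. The record form's untimed pre-operative assessment, completed by nursing staff including those on the wards, could be an earlier check, or could be O1 itself. Patients are on the routine surgical schedule and the study is explained to them beforehand, so earlier screening is feasible. This objection stands, and it limits the point to what the document leaves open.

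The route to bias is also narrow. It needs a one-sided mark, an assessor aware of the side, a different decision depending on the side, and a mark that persists and is graded as an injury. This also stands and is why the partial scenario matters.

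Two further arguments hold only in part. Exclusion item 4 speaks of an obvious phenomenon, which suggests that borderline marks are kept on either side. But inclusion item 6 rules out any pressure injury without that qualifier, so the threshold remains a judgement. The form's site and grade could separate an old mark from a new injury, but only if the baseline was recorded even-handedly.

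Finally, wrapping pads after induction would add time under anaesthesia, and a demand to analyse every assigned patient would collide with the under-2.5-hour exclusion. Both are fair, and the fix allows for them.

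**Conclusion.** The point holds in limited form. The protocol sets up the side before the only skin check it times, and it contains nothing to keep the side unknown when a one-sided mark is judged or the baseline is recorded. The split-body design removes patient-level imbalance but not this.

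The size cannot be known from the document. Under the assumed rates, partial selection gives about 0.5 to 2.5 points in favour of cotton and rejection at most about 5%. The all-or-none worst case gives about 2 to 10 points and rejection from about 4% to about one third. It would be wrong to read the upper figures as the expected error rate: they need complete one-way exclusion, every retained mark scored as an injury, and marks in 20% of candidates, none of which the protocol supports. The change is worth making because it is cheap and selective exclusion cannot be corrected later, not because a large bias has been shown. If a ward skin check already precedes disclosure of the side, saying so would largely resolve the point.

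**What to change.** - Amend the O1 note and the Positioning and intervention methods text in Protocol section 4 so that the skin check and eligibility are completed and recorded before the side is disclosed. The ward or holding area is preferable, so that no time under anaesthesia is added.
- State whether the record form's pre-operative assessment is O1 or a separate, earlier check.
- Keep the existing random-number list concealed until then, for example in sequentially numbered sealed envelopes held by someone who neither enrols patients nor does the skin check. Open the envelope, and wrap the pads on the assigned side, only after eligibility is recorded.
- Report every patient whose assignment was opened, with the reason for any later exclusion, and reconcile this with the under-2.5-hour exclusion in Protocol section 3.

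The cost is a wording change, a set of envelopes and a few minutes of set-up per case. No patients, visits or measurements are added beyond the pre-operative assessment already on the form.
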